| RATIONALE | We show that airway mucus plugs are strongly associated with measures of airflow obstruction in chronic severe asthma, and this association provides the rationale for testing whether a mucolytic drug (n-acetylcysteine, “Mucomyst”) can decrease mucus plug scores and improve FEV1 values in patients with asthma. It is perhaps surprising that inhaled NAC has not been tested in a clinical trial in asthma, but a significant reason has been the uncertainty outlined above for the role of mucus in chronic disease. Another factor has been that clinical trials of NAC in COPD and cystic fibrosis have not been consistently encouraging. However, these trials have not had a biomarker to select patients who might benefit and they have used orally administered NAC, which does not achieve detectable drug concentration in airway lining fluid ⁶ . Our proposal to test the efficacy of NAC in a specific patient subgroup identified by a biomarker (CT imaging) is timely and addresses a novel approach to asthma treatment. |
| STUDY DESIGN | This is a single arm, non-randomized interventional phase 4 study. |
| PRIMARY OBJECTIVE | The primary objective is to determine if inhaled NAC decreases mucus plugs and improves lung function in patients with asthma. |
| SECONDARY OBJECTIVES | The secondary objective is to determine the duration of benefit of inhaled NAC in asthma. |
| NUMBER OF SUBJECTS | 30 |

| | |
|---|---|
| 
SUBJECT SELECTION CRITERIA
 | 
Inclusion Criteria
 
 1. Male or female between the ages of 18 and 80 years of age at Visit 1 2. Written informed consent obtained from subject and ability for subject to comply with the requirements of the study. 3. Able to perform reproducible spirometry according to ATS criteria 4. Physiological evidence of airflow obstruction (FEV1 bronchodilator reversibility of $\geq 12\%$ or hyperreactivity to methacholine reflected by a methacholine PC20 ≤ 16 mg/mL) 5. Clinical history of asthma per patient report or medical record 6. Pre-bronchodilator FEV1 $> 35\%$ predicted 7. Post-bronchodilator FEV1 $> 40\%$ but $< 90\%$ predicted 8. Asthma requiring treatment with inhaled corticosteroids (ICS) for 3 months or greater 9. CT mucus score ≥ 5 
Exclusion Criteria
 
 1. Pregnant, breastfeeding, or unwilling to practice birth control during participation in the study. 2. Presence of a condition or abnormality that in the opinion of the Investigator would compromise the safety of the patient or the quality of the data. 3. Smoking of tobacco or other recreational inhalants in last year and/or > 10 pack-year smoking history 4. Current participation in an investigational drug trial 5. Other chronic pulmonary disorders, including (but not limited to) cystic fibrosis, chronic obstructive pulmonary disease, chronic bronchitis, vocal cord dysfunction (that is the sole cause of respiratory symptoms and at the PI's discretion), severe scoliosis or chest wall deformities that affect lung function, or congenital disorders of the lungs or airways 6. Unwillingness to follow study procedures 7. History of allergy or intolerance to study drug 8. Any other criteria that places the subject at unnecessary risk according to the judgment of the Principal Investigator |
| 
TEST PRODUCT, DOSE, AND ROUTE OF ADMINISTRATION
 | 
20% NAC (3 mL) and albuterol (.5 mL) Product will be administered every 4-6 hours for 5 days during an inpatient stay at the hospital. Medication will be delivered by inhalation via nebulizer.
 |
| 
CONTROL PRODUCT, DOSE
 | 
No control product
 |

| | |
|--|--|
| AND ROUTE OF ADMINISTRATION | |
| DURATION OF SUBJECT PARTICIPATION AND DURATION OF STUDY | Subjects will be in the study for up to 91 days. Screening: up to 14 days Treatment: 5 days (subjects to be admitted to the hospital) Follow-up: 3 months The total duration of the study is expected to be 24 months. Subject recruitment will happen on a rolling basis. |
| CONCOMITANT MEDICATIONS | Prohibited: 
 • thiols and thiol derivatives • activated charcoal • inhaled insulin |
| EFFICACY EVALUATIONS | |
| PRIMARY ENDPOINT | The primary endpoint is the FEV1. Post-treatment FEV1 will be compared to pre-treatment baseline values. |
| SECONDARY ENDPOINTS | Secondary efficacy endpoints include: 
 • CT mucus score • FVC • PEF (AM and PM) • Air trapping (RV/TLC ratio) • FeNO • Blood eosinophils |
| OTHER EVALUATIONS | |
| SAFETY EVALUATIONS | Incidence of adverse events |
| PLANNED INTERIM ANALYSES | No interim analysis is planned. |
| STATISTICS Primary Analysis Plan | The primary analysis is a paired t-test analysis of the % change in FEV1 from the start to the end of the one week treatment period with four times daily NAC (Mucomyst-20). The secondary analysis will be to determine how the change in FEV1 relates to the change in CT mucus score. |
| Rationale for Number of Subjects | We propose a sample size of 30, which will provide us with the power to examine the effect of NAC in a subgroup of individuals with asthma who have CT evidence of intraluminal mucus and to identify the CT mucus score that performs best as a biomarker of treatment response to NAC. Participants will be enrolled if their CT mucus scores are ≥ 5.0 . To calculate sample size for the one-week treatment period study, we used FEV1 measures from 219 adults with asthma published in Corren et al. NEJM, 2011 ¹ . The authors found that the standard deviation for the change in FEV1 in liters from day 1 to day |

| | |
|--|---|
| | 
7 was 19%. Using a standard deviation of 19 and a two-sided alpha of 0.05, we calculate a sample size of 30 to have 80% power to detect a change in FEV1 of 10% (a reasonable effect size because early studies of Pulmozyme in CF reported a 10% increase in FEV1 at day 3 of treatment).⁷
 |
|--|---|

1 BACKGROUND

Mucus plugging of the airway is consistently found in fatal asthma². Decades ago, Dunnill provided graphic descriptions in 20 cases of fatal asthma³ noting that "the cut surface of the lung showed a striking picture with numerous grey, glistening, mucous plugs scattered throughout the airway passages." He summarized that "pathologically, the outstanding feature of the asthmatic lung lies in the failure of clearance of the bronchial secretions." Others have confirmed these findings, and it is only a small minority of asthma deaths that are not associated with airway mucus impaction.

In non-fatal or near-fatal asthma exacerbations, segmental collapse of lung lobes due to luminal occlusion is common. Lavage of these cases yields abnormal mucus plugs in the form of airway casts⁴. The combination of airway narrowing from concentric smooth muscle contraction with luminal obstruction by mucus marks asthma as uniquely dangerous among airway diseases in its propensity for sudden and sometimes fatal exacerbations. The role of mucus as a cause of airflow obstruction in acute severe asthma suggested to us that mucus plugs plays a role in the pathophysiology of airflow obstruction in chronic severe asthma as well. This role has been hard to prove, however, in large part because of difficulty in showing that mucus occludes the lumen in chronic severe disease. Lungs are available at autopsy to show mucus occlusion in fatal asthma,

[figure not shown]

Figure 1: Intraluminal mucus in CT lung images of asthmatics. Mucus plugs in CT scan images (white arrows) were defined as complete occlusion of an airway lumen by mucus and were identified as tubular structures in longitudinal section with branching (A & B) or without branching (C) or as rounded opacities in cross-section (D). The latter were traced cephalad or caudad on adjacent slices to confirm their continuity with unoccluded bronchi (red arrow).

and it is notable that there is evidence of occlusion in asthmatics who die with asthma (rather than because of it)⁵. But the field has yet to be persuaded of a role for mucus in airway dysfunction in chronic forms of severe asthma.

1.1 Overview of Non-Clinical Studies

Against this background, the preliminary data we show in Figures 1 and 2 are very important, because we show how CT lung images can reveal mucus plugs in chronic severe asthma and how these plugs are associated with lower lung function. Specifically, we use CT imaging to uncover that a majority (58%) of asthmatics in the NHLBI Severe Asthma Research Program (SARP) have at least one lung segment with a mucus plug and 27% have more than four lung segments with mucus plugs. Notably, asthmatics with a high mucus score achieve a post albuterol FEV1 > 80% much less frequently than asthmatics who have a zero mucus score (Fig 3).

[figure not shown]

Figure 2. A. The CT mucus segment score is usually 0 in health but many asthmatics enrolled in the NHLBI Severe Asthma Research Program have scores above 0 with some as high as 15-19. B. The frequency distribution of mucus score in asthma shows that 42% of patients have a score of 0 (zero mucus score); among the remaining 58% of asthmatics, the median mucus score was 3.5, and we classified score between 0.5 and 3.5 as “low” and above 4.0 as “high”.

Examined another way, we find that all asthmatics with an FEV1 < 60% after albuterol treatment have abnormal mucus scores, whereas the majority of asthmatics with an FEV1 >80% with albuterol treatment have zero or low mucus scores (Fig 3). These data clearly implicate mucus plugs in the pathogenesis of airflow obstruction in asthma. One reason why this role for mucus plugging has been underappreciated in chronic severe asthma is that mucus-related symptoms are both insensitive and non-specific indicators of mucus.

2 STUDY RATIONALE

We show that airway mucus plugs are strongly associated with measures of airflow obstruction in chronic severe asthma, and this association provides the rationale for testing whether a mucolytic drug (n-acetylcysteine, “Mucomyst”) can decrease mucus plug scores and improve FEV1 values in patients with asthma. It is perhaps surprising that inhaled NAC has not been tested in a clinical trial in asthma, but a significant reason has been the uncertainty outlined above for the role of mucus in chronic disease. Another factor has been that clinical trials of NAC in COPD and cystic fibrosis have not been consistently encouraging. However, these trials have not had a biomarker to select patients who might benefit and they have used orally administered NAC, which does not achieve detectable drug concentration in airway lining fluid⁶. Our proposal to test the efficacy of NAC in a specific patient subgroup identified

[figure not shown]

Figure 3. Mucus scores in asthmatics with different FEV1 values (post 6-8 puffs of albuterol). Note that all asthmatics with an FEV1 <60% have abnormal mucus scores.

by a biomarker (CT imaging) is timely and addresses a novel approach to asthma treatment.

2.1 Risk / Benefit Assessment

Risk: Inhaled n-acetylcysteine (NAC) is approved for the treatment of mucus associated airway disease, including asthma. The main side effect from inhaled n-acetylcysteine (NAC) is bronchospasm. We find that co-administering NAC and albuterol effectively prevents excessive bronchoconstriction in asthmatic patients. Specifically, in ten asthmatics that were given doses of 20% NAC as high as 3 mL together with 3 mL of albuterol, the largest FEV1 decline was 6%.

Benefit: Mucus plugs cause airway obstruction and symptoms of dyspnea. The role of mucolytics in decreasing plugs and increasing FEV1 has not been well studied. Our preliminary data, utilizing CT imaging and a novel scoring system, can identify and target a subgroup of patients who may benefit from inhaled mucolytic treatment more so than the asthmatic population as a whole.

To minimize risk, study participants will be admitted to a medical-surgical ward in the hospital and given all treatments under the supervision of a registered nurse and the covering medical team. Our study team of experienced clinicians will be available as needed.

3 STUDY OBJECTIVES

3.1 Primary Objective

The primary objective is to determine if inhaled NAC decreases mucus plugs and improves lung function in patients with asthma.

3.2 Secondary Objectives

The secondary objective is to determine the duration of benefit of inhaled NAC in asthma and identify characteristics of those subjects who benefit from mucolytic treatment.

4 STUDY DESIGN

4.1 Study Overview

This is a single center, single arm, non-randomized trial in 30 patients with asthma who demonstrate mucus plugging on a screening CT lung scan. Following outpatient screening studies, each subject will be admitted for 6 days/5 nights and receive NAC mixed with albuterol by nebulizer four times daily. After the active treatment phase, the subjects will be followed for 3 additional months as outpatient to track changes in CT lung scans in the off treatment period. Total duration of participation will be four months. Total duration of the study is expected to be 2 years.

5 CRITERIA FOR EVALUATION

5.1 Primary Efficacy Endpoint

FEV1 will be the primary endpoint because it is the most robust measure of airflow obstruction in asthma. We will compare post-treatment FEV1 to pre-treatment baseline values.

5.2 Secondary Efficacy Endpoints

Secondary efficacy endpoints will include:

- CT mucus score
- FVC
- PEF (AM and PM)
- Air trapping (RV/TLC ratio)
- FeNO
- Blood eosinophils

5.3 Safety Evaluations

The most important safety evaluations will be those that monitor for evidence of NAC-induced bronchoconstriction. In this regard, our plan is to measure peak flow (PEF) before and after each treatment.

6 SUBJECT SELECTION

6.1 Study Population

Subjects with a diagnosis of asthma who meet the inclusion and exclusion criteria will be eligible for participation in this study.

6.2 Inclusion Criteria

1. Male or female between the ages of 18 and 80 years of age at Visit 1
2. Written informed consent obtained from subject and ability for subject to comply with the requirements of the study.
3. Able to perform reproducible spirometry according to ATS criteria
4. Physiological evidence of airflow obstruction (FEV1 bronchodilator reversibility of $\geq 12\%$ or hyperreactivity to methacholine reflected by a methacholine PC20 ≤ 16 mg/mL)
5. Clinical history of asthma per patient report or medical record
6. Pre-bronchodilator FEV1 $> 35\%$ predicted
7. Post-bronchodilator FEV1 $> 40\%$ but $< 90\%$ predicted
8. Asthma requiring treatment with inhaled corticosteroids (ICS) for 3 months or greater

9. CT mucus score ≥ 5

6.3 Exclusion Criteria

1. Pregnant, breastfeeding, or unwilling to practice birth control during participation in the study.
2. Presence of a condition or abnormality that in the opinion of the Investigator would compromise the safety of the patient or the quality of the data.
3. Smoking of tobacco or other recreational inhalants in last year and/or >10 pack-year smoking history
4. Current participation in an investigational drug trial
5. Other chronic pulmonary disorders, including (but not limited to) cystic fibrosis, chronic obstructive pulmonary disease, chronic bronchitis, vocal cord dysfunction (that is the sole cause of respiratory symptoms and at the PI's discretion), severe scoliosis or chest wall deformities that affect lung function, or congenital disorders of the lungs or airways
6. Unwillingness to follow study procedures
7. History of allergy or intolerance to study drug
8. Any other criteria that places the subject at unnecessary risk according to the judgment of the Principal Investigator

7 CONCURRENT MEDICATIONS

All subjects should be maintained on the same medications throughout the entire study period, as medically feasible, with no introduction of new chronic therapies.

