7.2 Prohibited Medications and Treatments

The following medications are prohibited during the study and administration will be considered a protocol violation.

- Thiols and thiol derivatives
- Activated charcoal
- Inhaled insulin

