9.1 Clinical Assessments

9.1.1 Concomitant Medications

All concomitant medication and concurrent therapies will be documented at Visits 1-4 and at early termination when applicable. Dose, route, unit frequency of administration, and indication for administration and dates of medication will be captured.

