10.13 Visit 12 (Day 91)

1. Perform and record vital signs.
2. Perform and record oximetry.
3. Perform and record urine pregnancy test.
4. Perform and record fractional exhaled nitric oxide (FeNO) measurement.
5. Perform and record spirometry.
6. Perform and record post-bronchodilator reversibility.
7. Obtain a CT scan of the thorax.

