10.15 Late Withdrawal Visit (After Visit 3 Completion)

1. Record any adverse experiences.
2. Record changes to concomitant medications.
3. Perform and record vital signs.
4. Perform and record oximetry.
5. Perform abbreviated physical examination.
6. Perform and record fractional exhaled nitric oxide (FeNO) measurement.
7. Perform and record spirometry.
8. Perform and record post-bronchodilator reversibility.
9. Collect blood sample for clinical laboratory tests.
10. Obtain a CT scan of the thorax.

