13 PROTOCOL VIOLATIONS

A protocol violation occurs when the subject or investigator fails to adhere to significant protocol requirements affecting the inclusion, exclusion, subject safety and primary endpoint criteria. Protocol violations for this study include, but are not limited to, the following:

- Failure to meet inclusion/exclusion criteria
- Use of a prohibited concomitant medication

Failure to comply with Good Clinical Practice (GCP) guidelines will also result in a protocol violation. The Sponsor will determine if a protocol violation will result in withdrawal of a subject.

When a protocol violation occurs, it will be discussed with the investigator and a Protocol Violation Form detailing the violation will be generated. This form will be signed by a Sponsor representative and the Investigator. A copy of the form will be filed in the site's regulatory binder and in the Sponsor's files.

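### Medication rules run to Day 91, but nothing scheduled after discharge records whether completers kept to them, so the 6-week and 3-month results cannot be confirmed as off-treatment

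*Protocol*

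**What the plan says.** **Rules for the whole study.** Protocol section 7: "All subjects should be maintained on the same medications throughout the entire study period, as medically feasible, with no introduction of new chronic therapies". Section 7.2 lists thiols and thiol derivatives under the statement "The following medications are prohibited during the study and administration will be considered a protocol violation". Section 13 repeats "Use of a prohibited concomitant medication" as an example of a violation.

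**Recording.** Section 9.1.1: "All concomitant medication and concurrent therapies will be documented at Visits 1-4 and at early termination when applicable". Visit 4 is Day 1. In section 10, medication is an item at Visits 1, 2, 2b, 3 and 4. The item "Record changes to concomitant medications" also appears at the two withdrawal visits (10.14, 10.15). It is absent from the lists for Visits 5 to 12 (10.6 to 10.13). Appendix 1 has no medication row for any visit.

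**Use of the late data.** A secondary objective (3.2) is to "determine the duration of benefit of inhaled NAC in asthma". Section 4.1 says "the subjects will be followed for 3 additional months as outpatient to track changes in CT lung scans in the off treatment period". The SAP assesses plug reappearance at 6 weeks and 3 months and puts both time points in its secondary analyses. Neither 15.3, 15.4 nor the SAP says how values that follow a medication change are handled.

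**The concern.** A rule that runs to Day 91 is paired with a record that, for a completer, stops at Day 1. The late visits are meant to show what remains of a five-day treatment once it has stopped. There is one arm and no blinding (8.1, 8.2), so a low mucus score or a raised FEV1 at Day 48 or Day 91 will be credited to the inpatient course. A participant who went on using NAC, or whose controller therapy was stepped up, could look the same.

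Continued NAC would lengthen the apparent benefit. A controller change could act either way, since it may improve lung function or mark a patient who was getting worse. Without a record, adherence to section 7 cannot be shown and violations of 7.2 cannot be reliably counted. Information not taken at the visit is hard to recover later.

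**Working it through.** **1. The plan's own figure.** Inputs from 15.6: SD 19, change of 10, two-sided alpha 0.05, power 80%. For a paired comparison, n = (SD × (z0.975 + z0.80) / change)² = (19 × (1.960 + 0.842) / 10)² = 28.3, so 29. Exact noncentral-t power with 30 is 79.6%. The stated 30 reproduces, and this point does not touch it.

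**2. What covers each period for a completer.**

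| Period | Scheduled medication record | Other source |
|---|---|---|
| Day -14 to Day 1 (Visits 1-4) | Yes | – |
| Days 1-6, inpatient | No | Hospital orders and administration record (8.3.2, 8.4); adverse event form |
| Day 6 to Day 91 (outpatient Visits 10-12) | No | Adverse event form only (9.1.17, 11.1) |

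The uncovered stretch is 91 − 6 = 85 days and three visits (Days 13, 48 and 91).

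**3. What the adverse event form would catch.** Section 11.1 has the investigator ask about adverse events at each visit, and treatment given for one is recorded. A steroid course for an exacerbation should therefore appear. Two things would not: NAC taken by choice, and a controller change with no associated adverse event.

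**4. Possible size for FEV1.** The documents give no rate for either, so these are assumptions: k of 30 participants hold a 10-point gain (the planning effect) at the late visit, and the rest have none. Shift in the mean = k × 10 / 30.

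| k | Shift (points) |
|---|---|
| 1 | 0.3 |
| 2 | 0.7 |
| 3 | 1.0 |
| 5 | 1.7 |

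For scale, if the protocol's 7-day SD of 19 also held at Day 91, the standard error would be 19 / √30 = 3.5 points. The shift is then about 0.1 (0.3 / 3.5) to 0.5 (1.7 / 3.5) of a standard error.

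**5. CT mucus score.** The documents give no SD or expected change for it, so no comparable figure can be derived. If reappearance were reported as a proportion, which the SAP does not specify, each participant kept clear by continued NAC would move it by 1/30 = 3.3 percentage points.

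**The case against.** **The visit lists are incomplete, so their silence proves little.** This is fair. None of the lists for Visits 1 to 12 has an adverse event item, although 11.1 requires the question at every visit, and Appendix 1 omits medication even where 9.1.1 requires it. But the gap does not rest on silence: 9.1.1 names the visits at which medication is documented, and the lists agree with it.

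**Other contacts would bring changes to light.** Staff phone participants before medication-withholding visits, which 9.1.2 links to Visits 10 and 11 among others. Asthma drugs will be discussed, but no record is specified, and Table 2 does not list NAC, inhaled corticosteroids or systemic steroids. Section 13 provides a violation form, but only once a violation is known.

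**Continued NAC is unlikely.** It is barred, it is dispensed on the ward, and no take-home supply is described. This lowers the probability and stands as a limit on the point. Still, 2.1 describes inhaled NAC as already approved for asthma, participants know what they received, and section 7 is qualified by medical feasibility.

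**Stronger readings that the documents do not support.**
- A reader might infer that steroid courses in follow-up go unrecorded, and size the gap by an assumed exacerbation rate. Most such courses should be on the adverse event form, so a count of courses does not measure what is missing.
- A reader might count the gap from Day 1 and include the primary endpoint. The hospital record covers the inpatient days.
- A reader might see a clean contrast in which late withdrawers are asked about medication and completers are not. Section 10.15 suggests this, but 12.2 gives those leaving after Visit 8 and before Visit 11 the procedures of their next scheduled visit, which has no medication item.

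**Conclusion.** The point holds for the outpatient follow-up. From Day 6 to Day 91 no scheduled item for a completer would record voluntary NAC use or a controller change made without an adverse event, although both are restricted for the whole study and the late results depend on their absence. What is exposed is the duration-of-benefit objective at Days 48 and 91. The baseline to Day 6 FEV1 comparison is little affected.

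The likely size for FEV1 is modest: a shift of 0.3 to 1.7 points if 1 to 5 of 30 participants held a 10-point gain. Both the count and the gain are assumed. The case for change does not depend on them, because the present plan has no scheduled means of finding out the true number. This is a worthwhile, low-cost improvement to data collection and does not undermine the primary result.

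**What to change.** **Protocol.** Extend 9.1.1, and add to 10.11, 10.12 and 10.13, the item already used at Visits 2 to 4: "Record changes to concomitant medications". Add a medication row to Appendix 1 for Visits 1-4 and 10-12. At Visits 10, 11 and 12 ask directly about NAC or other thiols, systemic corticosteroids, and controller or biologic changes since the last visit. Treatment, eligibility and sample size stay as they are.

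**SAP.** State that observed values are used in the main analyses at Days 48 and 91. Report how many participants had each kind of change, drawing on the new item and the adverse event form. Repeat both analyses without those participants as a sensitivity check.

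**Cost.** Three visits × 30 participants = 90 short CRF entries at visits already scheduled, and a few SAP sentences. Self-report can miss use. Excluding treated participants may remove those who did worst, so the check can look favourable and must be read beside the main analysis. It also costs power: at the planning values (change 10, SD 19, set for the one-week comparison and used here only as a guide), exact power is 79.6% with 30, 76.6% with 28 and 69.5% with 24.
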